7.1. Scale and Duration

Subjects will be enrolled at up to 85 centers in the United States, Canada, Australia, and Europe. There will be up to 2820 subjects total in ACURATE IDE. It is expected that >80% of enrolled subjects will be from the United States. To achieve sufficient distribution of lower risk subjects in the Main Randomized Cohort, there will be \geq 30% intermediate risk randomized subjects and \geq 35% low risk randomized subjects enrolled (please see definition of operative risk in Section **25.2**).

The ACURATE IDE study cohorts include the following.

- Main Randomized Cohort: A prospective, multicenter, 1:1 randomized controlled trial (RCT; ACURATE versus a commercially available balloon-expandable SAPIEN 3TM Transcatheter Heart Valve or future iteration [SAPIEN 3; Edwards Lifesciences LLC, Irvine, CA, USA] or a commercially available self-expanding CoreValve[®] Transcatheter Aortic Valve Replacement System, CoreValve[®] Evolut[™] R Recapturable TAVR System, EVOLUT[™] PRO System, or future iteration [CoreValve; Medtronic, Inc., Dublin, Ireland]). There will be 1500 subjects in the RCT.
- **Roll-In Cohort:** A non-randomized Roll-In phase with the test device. Centers that do not have implantation experience with the ACURATE *neo*TM bioprosthesis

(transfemoral delivery) will perform at least 2 Roll-In cases with ACURATE *neo2* before commencing treatment in the Main Randomized Cohort (up to 170 Roll-In subjects in total). Centers with prior experience with ACURATE are not required to do Roll-In cases. Data from Roll-In subjects will be summarized separately from the Main Randomized Cohort and will not be included in the primary endpoint analysis.

- **4D CT Imaging Substudy:** Select centers with the ability to perform high quality 4D computed tomography (CT) scans will include subjects (minimum of 200) from the Main Randomized Cohort in a 4D CT Imaging Substudy to assess the prevalence of reduced leaflet mobility and hypoattenuated leaflet thickening (HALT)⁷³ and the relationship, if any, to clinical events. Centers should ask all eligible subjects to consider participation in the substudy.

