	physical activity. They are comfortable at rest. Ordinary physical
	activity results in fatigue, palpitation, dyspnea, or anginal pain.Class IIISubjects with cardiac disease resulting in marked limitation of
	physical activity. They are comfortable at rest. Less than
	ordinary physical activity causes fatigue, palpitation, dyspnea, or
	anginal pain.
	Class IV Subjects with cardiac disease resulting in inability to carry on
	any physical activity without discomfort. Symptoms of cardiac insufficiency or of the anginal syndrome may be present even at
	rest. If any physical activity is undertaken, discomfort is
	increased.
NONSTRUCTURAL	Any abnormality not intrinsic to the valve itself that results in stenosis or
DYSFUNCTION	regurgitation of the operated valve or hemolysis. The term nonstructural
	dysfunction refers to problems (exclusive of thrombosis and infection) that do not
	directly involve valve components yet result in dysfunction of an operated valve, as diagnosed by re-operation, autopsy, or clinical investigation. Nonstructural
	dysfunction includes the following.
	• Entrapment by pannus, tissue, or suture
	Paravalvular leak
	• Inappropriate sizing or positioning
	• Residual leak or obstruction after valve implantation or repair
	Clinically important intravascular hemolytic anemia
	• Development of aortic or pulmonic regurgitation as a result of technical errors
	• Dilatation of the sinotubular junction
	• Dilatation of the valve annulus after either valve replacement with stentless
	prostheses, new onset of coronary ischemia from coronary ostial obstruction,
	or paravalvular aortic regurgitation

	Table 23.2-1. Definitions
Term	Definition
OPERATIVE RISK ⁶⁷	Operative risk is determined by a center cardiac surgeon and must be confirmed by the Case Review Committee (including a cardiac surgeon). Low: Estimated 30-day risk of mortality is < 3% Intermediate: Estimated 30-day risk of mortality is 3–10% High: Estimated 30-day risk of mortality is >10–15% Very High: Estimated 30-day risk of mortality is >15% Extreme: Estimated 30-day risk of irreversible morbidity or mortality is ≥50%
PARAVALVULAR REGURGITATION	Leakage due to a separation of the prosthetic valve from the annulus. Any evidence of leakage of blood around the device. Diagnosis of paravalvular regurgitation may be obtained from TEE/TTE, however, definitive diagnosis is obtained at re-operation, explant, or autopsy.

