## 3.1.2 Sample Size

Although the primary endpoint analysis is performed using the Bayesian method, the sample size calculation for the Main Randomized Cohort is based on a standard non-inferiority two-sample test approach with one formal interim analysis planned. The sample size calculation for the primary endpoint is based on the following assumptions.

- Expected rate for both arms = 22.3% (based on a weighted average of TAVR data
- Non-inferiority margin ( $\Delta$ ) = 8.0% (36% relative to expected rate)
- Test significance level ( $\alpha$ ) = 0.025 (1-sided)
- Test (ACURATE): Control ratio = 1:1
- Power  $(1 \text{ minus } \beta) > 90\%$
- Expected rate of attrition = 5%
- Total sample size = 1500 (750 per group)
- Number of evaluable subjects per group = 712
- Analyses: One administrative, one formal interim, one final

The Pocock-type method is used during sample size calculations when 70% subjects reached 1-year follow-up at the formal interim analysis. The statistical software EAST® 6.5 is used for the sample size calculations.

The estimated proportions of subjects in the Main Randomized Cohort by operative risk level are 10% extreme risk, 25% high risk, 30% intermediate risk, and 35% low risk.

The formal interim analysis will be carried out after enrollment in the Main Randomized Cohort is completed. This formal interim analysis will be conducted on the full N=1500 subjects of the Main Randomized Cohort after first 1050 subjects in the Main Randomized Cohort have completed 1-year follow-up or at least 80% low risk subjects in the Main Randomized Cohort have completed 6-month follow-up, whichever comes later. The piecewise exponential models will be based on outcomes among these subjects who have completed 30-day, 6-month, or 1-year follow-ups. The results from the models will be used to estimate the 1-year results by treatment group through Bayesian posterior probabilities for the non-inferiority test. The final analysis for the primary endpoint will be performed on all subjects with completed 1-year data if non-inferiority cannot be claimed at the formal interim analysis.

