#### 3.1.5.4 Bayesian method for the hypothesis test

For each Bayesian piecewise exponential model, 10000 posterior samples for each  $\lambda_{i,j,k}$  are generated, the estimated 1-year primary endpoint event rates (PE\_ACURATE and PE\_Control) for each sample of  $\lambda_{i,j,k}$  can be calculated based on the following:

Form/Template 90702621 Rev/Ver AF ACURATE IDE SAP 92400558, Rev/Ver I Page 28 of 64

$$\begin{aligned} &\text{PE}_{\text{ACURATE, E/HR}} = 1 - e^{-(31*\lambda_{1,1,1} + 150*\lambda_{1,1,2} + 185*\lambda_{1,1,3})}, \\ &\text{PE}_{\text{Control, E/HR}} = 1 - e^{-(31*\lambda_{2,1,1} + 150*\lambda_{2,1,2} + 185*\lambda_{2,1,3})}, \\ &\text{PE}_{\text{ACURATE, IR}} = 1 - e^{-(31*\lambda_{1,2,1} + 150*\lambda_{1,2,2} + 185*\lambda_{1,2,3})}, \\ &\text{PE}_{\text{Control, IR}} = 1 - e^{-(31*\lambda_{2,2,1} + 150*\lambda_{2,2,2} + 185*\lambda_{2,2,3})}, \\ &\text{PE}_{\text{ACURATE, LR}} = 1 - e^{-(31*\lambda_{1,3,1} + 150*\lambda_{1,3,2} + 185*\lambda_{1,3,3})}, \\ &\text{PE}_{\text{Control, LR}} = 1 - e^{-(31*\lambda_{2,3,1} + 150*\lambda_{2,3,2} + 185*\lambda_{2,3,3})}, \end{aligned}$$

The overall weighted 1-year primary endpoint rates for each sample from the posterior distributions are calculated as the following:

 $PE_{ACURATE} = 35\%* PE_{ACURATE, E/HR} + 30\%* PE_{ACURATE, IR} + 35\%* PE_{ACURATE, LR} PE_{Control} = 35\%* PE_{Control, E/HR} + 30\%* PE_{Control, IR} + 35\%* PE_{Control, LR}$ The treatment difference (PE\_ACURATE minus PE\_Control) will be calculated. Iterating this sampling process for 10000 times over the posterior distributions of the lambdas, the posterior distributions of the primary endpoint rate by treatment group and the posterior distribution of the treatment difference can be constructed for the hypothesis test on the primary endpoint. Similarly, the credible intervals will be constructed based on these posterior distributions. The non-inforiority test then is performed based on the prespecified success criteria: the posterior probability of H1 given the observed interim data is greater than the threshold  $\xi$ . If the posterior probability is greater than the pre-specified threshold  $\xi$ , then the non-inferiority is declared. To be specific, if the posterior probability of the treatment difference (PE\_ACURATE minus PE\_Control) <  $\Delta$  constructed from the sampling distribution (N=10000) is greater than the pre-specified threshold  $\xi$ , then the non-inferiority is declared.

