Model 2 and 3 results will be combined using the weighted method to estimate the primary endpoint rate. The weights are proportional to the numbers of observations between the control devices (CoreValve vs SAPIEN) from the observed data that are used to fit each model. The weights are w1/(w1+w2) and w2/(w1+w2) for Model 2 and Model 3, respectively. With the sampling of posterior distributions of the hazards, the hypothesis can be tested.

Sensitivity analysis may be performed using the observed weights for the operative risk cohorts. The weights are proportional to the numbers of observations between the operative risks (extreme/high, intermediate, and low) from the observed data that are used to fit each model. The sensitivity analysis is based on the exact same data set used in the main primary endpoint analysis.

Note: the sensitivity analyses, tipping point analyses, or analyses involved the piecewise exponential modes may be adjusted based on the pre-specified methods (e.g. if pre-specified the number of events are too small for a piecewise exponential model, which causes the model not converged. The number of intervals or number of models or other related parameters may be reduced or adjusted accordingly.)

Reference: SAS Manual,

https://support.sas.com/documentation/onlinedoc/stat/131/phreg.pdf

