#### 3.1.9 Bayesian Design Operating Characteristics

#### 3.1.9.1 Simulation setup

Piecewise exponential model:

1) Time intervals follow the actual follow-up visits defined in the protocol, which are the intervals as 0 - 30 days, 31 - 180 days, and 181 - 365 days post randomization for the ITT analysis.

2) Hazard rate within each time interval is constant. The hazard rates may be different between different intervals. The following is the hazard function defined by different treatment groups:

 $h_{j}(t) = \begin{cases} \lambda_{j,1}, & 0 \le t \le 30 \ days \\ \lambda_{j,2}, & 31 \le t \le 180 \ days \\ \lambda_{j,3}, & 181 \le t \le 365 \ days \end{cases}$ 

Where j=1 or 2 for the test and the control groups within each risk stratum, respectively.

3) SAS Programming Software and the Procedure PROC MCMC are used for simulation and the Bayesian analyses.

Note: the piecewise exponential models are constructed by risk stratum, treatment group, and time interval. The parameters to be estimated are specified in Section 3.1.5.2 Table 1.

Simulation parameters

- 1) Proper and reasonably non-informative prior Gamma (shape=0.0001, inverse-scale=0.0001)
- 2) Assumption of number of subjects available for each time interval at the time of the interim analysis by risk stratum for each treatment group (total N=750 per treatment group) (Table 2).

Risk Stratum	30-Day	6-Month	1-Year
E/HR	262	241	194
IR	225	225	221
LR	262	223	115

Table 2. Available Data for Simulations at Interim for each treatment group

- 3) Expected rate for the Control (22.3%)
- 4) Expected rate for the Test (30.3% for alpha, 22.3% for the power).
- 5) Hazard rates assumptions by the time intervals as following (Table 3):

 Table 3. Cases for the Relationship between Lambdas for Simulations

Hazard assumptions*	λ2	λ3	
Case 1	0.4*λ1	0.3*λ1	
Case 2	0.3*λ1	0.2*λ1	
Case 3	0.3*λ1	0.1*λ1	
Case 4	0.2*λ1	0.2*λ1	

\*The assumptions are estimated based on historical data for event rates at 30-day, 6month, and 1-year (Table 4).

#### Form/Template 90702621 Rev/Ver AF ACURATE IDE SAP 92400558, Rev/Ver I Page 32 of 64

Clinical Study	Device	Risk Profile	Available Event	Event rate by time 30d vs 6m vs 12m	Estimated Lambdas (λ1, λ2, λ3)
Partner 2B	SAPIEN XT	Extreme	death/major stroke/rehosp	17% vs 28% vs 37%	λ2=0.15*λ1 λ3=0.12*λ1
CoreValve ER	Corevalve	Extreme	death/major stroke	10% vs 19% vs 26%	λ2=0.19*λ1 λ3=0.14*λ1
Partner 1A	SAPIEN	High	death/major stroke	7% vs 18% vs 26%	λ2=0.33*λ1 λ3=0.23*λ1

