				Final	0.75%	0.80%	0.85%	0.80%	
				Interim	2.40%	2.30%	2.15%	2.10%	
30.30%	22.3%	λ2=0.3*λ1 λ3=0.1*λ1	[0, 180] [181, 270] [271,365]	Final	0.95%	0.90%	0.90%	0.90%	

Table 6. Sensitivity Analysis for Type I Error by Time Interval

\* Intervals used for creating sample data. The models used the intervals: [0,30], [31, 180], [181, 365] as prespecified for the primary endpoint analysis.

The study power (1-minus type II error) is more than 90% at the interim or the final analysis of the primary endpoint from the simulation results as shown in Table 6. The study is sufficiently powered for the primary endpoint analysis.

	Simulation	Chance of the Posterior Probability for Test Rate minus Control Rate <8% is greater than ξ						
Test Rate	Control Rate	Hazard Rate	Time Interval	Time	ξ=97.1%	ξ=97.3%	ξ=97.5%	ξ=97.7%
	22.3%	$\lambda 2=0.3*\lambda 1 \ \lambda 3=0.2*\lambda 1$	[0, 30] [31, 180] [181,365]	Interim	95.65%	95.45%	95.15%	94.70%
22.30%				Final	97.50%	97.40%	97.05%	96.85%

Table 6. Simulation Results for Study Power

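### Does giving extreme/high risk a fixed 35% weight, with no enrolment minimum for that stratum, leave the trial short of power?

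*SAP*

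**What the plan says.** The primary analysis estimates a 1-year rate in each risk stratum and arm, then combines them: "The overall weighted 1-year primary endpoint rates for each sample from the posterior distributions are calculated as the following" (SAP 3.1.5.4). The weights are 35/30/35 for extreme/high, intermediate and low risk, whatever mix is enrolled. SAP 3.1.6 uses the same model and threshold at the final analysis.

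The weights match the planning assumption in SAP 3.1.2: "The estimated proportions of subjects in the Main Randomized Cohort by operative risk level are 10% extreme risk, 25% high risk", with 30% intermediate and 35% low. Protocol 7.1 turns part of that assumption into enrolment rules. It opens with "To achieve sufficient distribution of lower risk subjects in the Main Randomized Cohort" and sets at least 30% intermediate and at least 35% low. Extreme/high has no minimum.

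The simulations use one mix. SAP 3.1.9.1, Table 2 is headed "Assumption of number of subjects available for each time interval at the time of the interim analysis by risk stratum for each treatment group" and has 262/225/262 subjects per arm at 30 days. SAP 3.1.9.2 then states: "The study power (1-minus type II error) is more than 90% at the interim or the final analysis of the primary endpoint", with 95.15% at the interim and 97.05% at the final at the 97.5% threshold. SAP 3.1.7 adds: "Sensitivity analysis may be performed using the observed weights for the operative risk cohorts".

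**The concern.** The two minimums can only push the mix one way. They can raise the lower-risk shares and shrink extreme/high, the one stratum with no minimum, while its weight stays at 35%. Any extreme/high share from 0 to 35% complies with the protocol. That stratum probably has the highest event rate, so it dominates the variance even at the planned share, and more so as it thins.

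The stake is power. A truly equivalent device could miss non-inferiority with all 1500 subjects enrolled, and a reader would find no table showing how power depends on the mix. An enrolment minimum for extreme/high, a grid of power by mix, and a mandatory observed-weights analysis all look cheap.

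**Working it through.** **Inputs.** Weights 35/30/35 (SAP 3.1.5.4); margin 8 points, 750 per arm, 712 evaluable (SAP 3.1.2); threshold 97.5% (SAP 3.1.9.2); hazards λ2 = 0.3λ1 and λ3 = 0.2λ1, with Table 2 follow-up at the interim (SAP 3.1.9). The documents give no stratum rates for the simulations. Assumption: 37%, 21.2% and 8.5%. The outer two are the extreme-risk and low-risk composite rates in SAP Table 4, and the middle one brings the weighted rate to plan: 0.35×37 + 0.30×21.2 + 0.35×8.5 = 22.3%.

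**Reproducing the plan's figure.** Simulating the SAP model at the planned mix with these rates gives 94.3–95.6% interim and 97.0–97.6% final over repeat runs (SAP: 95.15% and 97.05%). Flat 22.3% rates give only 91.1–92.5% at the interim, so they do not match.

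**Closed-form check, final look.** Power = Φ(0.08/SE − 1.96), with SE² = (2/n) Σ w²p(1−p)/f, where f is the enrolled share. The terms w²p(1−p) are 0.02855, 0.01504 and 0.00953.

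- Planned mix: 0.02855/0.35 + 0.01504/0.30 + 0.00953/0.35 = 0.0816 + 0.0501 + 0.0272 = 0.1589. SE = √(2×0.1589/750) = 0.0206; power = Φ(1.93) = 97.3%. Extreme/high supplies 0.0816/0.1589 = 51% of the variance.
- Extreme/high at 20%, low risk at 50%: 0.1428 + 0.0501 + 0.0191 = 0.2119. SE = 0.0238; power = Φ(1.41) = 92.0%; variance share 67%.
- Extreme/high at 15%, low risk at 55%: sum 0.2578, SE = 0.0262, power = Φ(1.09) = 86.2%; variance share 74%.

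**Simulated power**, 750 per arm, equal true rates, unequal stratum rates as above (ranges over repeat runs):

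| Extreme/high share | Interim | Final alone | Either look |
|---|---|---|---|
| 35% | 94.3–95.6% | 97.0–97.6% | 97.7–98.1% |
| 20% | 87.5–89.5% | 91.6–93.4% | 92.7–93.7% |
| 18% | 85.7–86.9% | 90.3–91.9% | 91–93% |
| 15% | 80.5–83.2% | 85.9–89.0% | 87.8–89.5% |
| 10% | 69.1% | 74.4–75.8% | 77.1% |

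**Where 90% is crossed.**

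- Either look: roughly 15–17%.
- Final look alone, closed form, unequal rates: 16.7–17.9% at 750 per arm and 18.1–19.4% at 712, depending on which stratum takes the vacated places.
- Final look alone, closed form, flat rates: 14.9–15.6% at 750 and 16.4–17.2% at 712.
- Interim: about 22–23% if Table 2's follow-up fractions are kept.

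**Interim timing.** Table 2 implies 2×(194 + 221 + 115) = 1060 one-year completers. At a 20% share with low risk taking the excess, the same fractions give 2×(150×194/262 + 221 + 375×115/262) = 2×(111.1 + 221 + 164.6) = 993. That is short of the 1050 required by SAP 3.1.5.2, so the look would wait. Scaling follow-up to 1050 moves the interim crossing to about 21%.

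**The case for a change.** The best case for a change is that the sponsor judged the risk mix worth controlling for two strata and left open the one that carries half the variance. Risk class is already settled before randomisation ("Operative risk is determined by a center cardiac surgeon and must be confirmed by the Case Review Committee"), so a third minimum is workable. At 20% (300 of 1500) it would hold closed-form final-look power at about 91–94% across the scenarios tried. The SAP also claims more than 90% at the interim, which is the first figure to be lost.

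The structural facts stand, and so does the direction of the effect. Three points limit them. First, SAP 3.1.3 allows non-inferiority at either look, so the relevant power is success at either; at an 18% share that is still 91–93%. Second, the SAP's power is stated for the mix it simulates and is right there. Third, the remedies gain little. A minimum is idle at the planned mix and, when it binds, closes lower-risk places and prolongs enrolment, against the purpose stated in Protocol 7.1. A mix grid changes no result. Results by operative risk are already planned in SAP 5.4, so making the observed-weights analysis mandatory only firms up a supplementary analysis.

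One uncertainty remains. The final-look type I errors in SAP Table 5 (0.55–0.95% at the chosen threshold) look like success at the final after failing the interim; a stand-alone final look in this model gives about 2.65%. The 97.05% may therefore be cumulative rather than stand-alone. The simulated values at the planned mix, 97.0–97.6% alone and 97.7–98.1% at either look, are close enough that the conclusion does not depend on this.

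**Conclusion.** No change is needed. Fixed weights keep the estimand and the 8-point margin tied to the planned population, and the comparison within strata is unbiased at any mix. The only exposure is lost precision under a drift that no document predicts. Extreme/high would have to fall from 525 planned subjects to roughly 225–255 (15–17% of 1500) before the chance of success at either look drops below 90%. The final look alone crosses at about 15–19%, and the interim at about 21–23%. These figures assume equal true rates in the two arms and stratum rates that the documents do not supply; they also move with the number evaluable and with which stratum takes the vacated places. An extreme/high minimum is a fair option for the sponsor to set against slower enrolment. Its absence is not an error. A table of power by mix would help readers but would alter no analysis.

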#### 3.1.6 Final Analysis

If non-inferiority has been declared at the formal interim analysis, the non-inferiority test will not be performed at the final analysis. Otherwise, the non-inferiority test will be performed at the final analysis using Bayesian method when all subjects have completed 1-year data. As it has been formulized in the Section 3.1.3, the same piecewise exponential model and pre-specified success criteria are used. If the posterior probability of H1 given the observed data is greater than pre-specified threshold  $\xi$ , then the non-inferiority is declared at the final analysis for the primary endpoint.

#### 3.1.7 Sensitivity Analyses for Primary Endpoint

Handling of dropouts and missing data will depend on their frequency and the nature of the outcome measure. Sensitivity analyses (e.g., tipping-point analysis) will be performed

to assess the impact of subjects with inadequate follow-up (i.e., missing data) on the primary endpoint and to assess the robustness of the conclusion of the primary analysis. The tipping-point analysis is based on the exact same data set used in the main primary endpoint analysis. A patient is considered as having missing primary endpoint data when the patient's last day in the study is less than 335 days post-randomization without occurrence of any primary endpoint events, e.g.: patients withdrew, lost to follow up, or had 1-year visit prior to reaching 335 days post-randomization and had no primary endpoint events. In the tipping point analysis, these patients will be considered as not having sufficient follow-up days. The tipping-point analysis will impute the primary endpoint event occurred one day post censoring (days to imputed primary endpoint event) for the subject with not sufficient 1-year follow-up. The missing cases will be imputed by the chronological order of the imputed days to the primary endpoint event and then by the randomization date or procedure date. The tipping point analysis assumes the subject with missing data will develop a primary endpoint event at the time of the last follow-up days (<335 days) for the test arm, but not develop any primary endpoint event for the control arm. The tipping point analysis results will show how many more subjects on average in the test arm could develop a primary endpoint event while the study could still declare the non-inferiority. The tipping point table and plot will be provided to demonstrate the robustness of the conclusion of the primary endpoint hypothesis test. Tipping point analysis will use the same Bayesian approach. Tipping point analysis will be provided only when the non-inferiority is declared at either the interim or the final.

The time intervals of the main piecewise exponential model are based on the actual study follow-up visits defined in the protocol (such as: 30-day, 6-month, and 1-year). The time interval sensitivity analyses will be based on the exact same data set that the main primary analysis will be conducted on. For this sensitivity analysis, each time interval (such as: 0-30 days, 31-180 days, and 181-365 days) will be partitioned into two intervals with approximately equal number of events. The Proc PHREG procedure will be used. The additional sensitivity analysis using different time intervals between 0-365 days (eg: the SAS default from the Proc PHREG procedure that partitions the time axis into eight intervals with approximately equal number of events in each interval when appropriate) for the piecewise exponential model may be performed for the primary endpoint analysis. This sensitivity analysis will only be performed on all the patients who completed the 1year visits. For each individual model, if the model with eight intervals by default doesn't exist, number of intervals will be reduced to four intervals. If model with four intervals still doesn't exist, the number of intervals for the model will be reduced by one each time until a valid model is identified. Partitions and number of time intervals between different models could be different.

In the main analysis using Bayesian approach, subjects are considered exchangeable between the earlier enrolled and the later enrolled. Thus, the assumption is that the subject characteristics are distributed at random over the enrollment time. In order to check the model robustness, sensitivity analysis for the primary endpoint may be performed with piecewise exponential model adjusting for key covariates, such as: control devices for the control arm only (CoreValve or SAPIEN 3). The sensitivity analysis for the control devices will fit three piecewise exponential models based on the following groups of subjects.

- 1. Test group subjects by risk strata and time intervals
- 2. CoreValve subjects by risk strata and time intervals (N=w1 subjects)
- 3. SAPIEN 3 subjects by risk strata and time intervals (N=w2 subjects)

Model 2 and 3 results will be combined using the weighted method to estimate the primary endpoint rate. The weights are proportional to the numbers of observations between the control devices (CoreValve vs SAPIEN) from the observed data that are used to fit each model. The weights are w1/(w1+w2) and w2/(w1+w2) for Model 2 and Model 3, respectively. With the sampling of posterior distributions of the hazards, the hypothesis can be tested.

Sensitivity analysis may be performed using the observed weights for the operative risk cohorts. The weights are proportional to the numbers of observations between the operative risks (extreme/high, intermediate, and low) from the observed data that are used to fit each model. The sensitivity analysis is based on the exact same data set used in the main primary endpoint analysis.

Note: the sensitivity analyses, tipping point analyses, or analyses involved the piecewise exponential modes may be adjusted based on the pre-specified methods (e.g. if pre-specified the number of events are too small for a piecewise exponential model, which causes the model not converged. The number of intervals or number of models or other related parameters may be reduced or adjusted accordingly.)

Reference: SAS Manual,

https://support.sas.com/documentation/onlinedoc/stat/131/phreg.pdf

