#### 3.1.5.2 Formal interim analysis cutoff date and analysis cohorts

A cutoff date for the interim analysis is the date when the first 1050 subjects in the Main Randomized Cohort have completed a 1-year follow-up or at least 80% low risk subjects in the Main Randomized Cohort have completed a 6-month follow-up, whichever comes later. All subjects who have completed 30-day, 6-month, or 1-year (defined in Section 3.1.5.1) prior to or on the cutoff date should be included in the 30-day, 6-month, or 1year analysis cohort, respectively. The three analysis cohorts will be used for the piecewise exponential models for different time intervals, defined as the following:

- 30-day analysis cohort will be used for piecewise exponential models between 0-30 days.
- 6-month analysis cohort will be used for piecewise exponential models between 31-180 days.
- 1-year analysis cohort will be used for piecewise exponential models between 181-365 days.

Note: the analysis cohorts (30-day, 6-month, 1-year) are for ITT analysis. The analysis cohorts for the Implanted analysis will the subset of the ITT set for subjects who meet the Implanted definition.

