The analysis set at the formal interim is the subset of randomized subjects who had completed 30-day, 6-month, and/or 1-year follow-up as defined in Section 3.1.5.1. The analysis set (N=1500) at the final will include all enrolled subjects.

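### The tipping-point rule in SAP 3.1.7 does not separate dropouts from subjects still in follow-up at the formal interim, so an interim tipping count may not measure robustness to dropout.

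*SAP*

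**What the plan says.** SAP 3.1.7 opens by discussing dropouts and missing data, then gives an operational rule: a subject is missing when the "last day in the study is less than 335 days post-randomization without occurrence of any primary endpoint events". The illustrations are "patients withdrew, lost to follow up, or had 1-year visit prior to reaching 335 days post-randomization and had no primary endpoint events". They are introduced as examples and do not limit the rule.

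Three further statements fix where the rule applies.

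- Data: "The tipping-point analysis is based on the exact same data set used in the main primary endpoint analysis".
- Timing: "Tipping point analysis will be provided only when the non-inferiority is declared at either the interim or the final".
- Method: the analysis "will impute the primary endpoint event occurred one day post censoring", in the test arm only, working through cases in chronological order of the imputed event day.

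On the interim data set, SAP 4.2 says "The analysis set at the formal interim is the subset of randomized subjects who had completed 30-day, 6-month, and/or 1-year follow-up". SAP 3.1.5.2 assigns a cohort to each interval. It begins with "30-day analysis cohort will be used for piecewise exponential models between 0-30 days" and continues with 6-month completers for days 31 to 180 and 1-year completers for days 181 to 365. SAP 3.1.6 says the non-inferiority test is not repeated once non-inferiority has been declared at the interim.

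**The concern.** The interim set is built to include people whose year is not over. They are event-free, their last recorded day is below 335, and they satisfy the stated definition although nobody withdrew or was lost. The rule has no condition that tells follow-up not yet due from follow-up that was lost. Because imputation runs in order of censoring day, ongoing subjects with short follow-up would be turned into test-arm events before later true dropouts.

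A tipping-point table should tell a reader how much withdrawal and loss could change the conclusion. If the pool is mostly ongoing subjects, the count answers a different question. The interim is also the likely place for it to be produced: the SAP's power simulation (SAP 3.1.9.2) puts interim success at 95.15% with equal rates and the 97.5% threshold. On that path, no later non-inferiority test is planned.

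**Working it through.** **Inputs from the documents.** SAP Table 2 gives, per arm, for "Assumption of number of subjects available for each time interval at the time of the interim analysis":

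| Risk stratum | 30-day | 6-month | 1-year |
|---|---|---|---|
| Extreme/high | 262 | 241 | 194 |
| Intermediate | 225 | 225 | 221 |
| Low | 262 | 223 | 115 |
| Sum | 749 | 689 | 530 |

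Other inputs are 750 per arm, 5% attrition, a 22.3% event rate, and Case 2 hazards (λ2 = 0.3 λ1, λ3 = 0.2 λ1).

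**The plan's own figures first.** 750 × 0.95 = 712.5, which matches the stated 712 evaluable per group. 2 × 530 = 1060, which agrees with the trigger of 1050 subjects at 1 year. Table 2 is therefore a fair picture of the planned interim.

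**Subjects short of 1 year, per arm.** 749 − 530 = 219. Of these, 689 − 530 = 159 are past 6 months and 749 − 689 = 60 are between 30 days and 6 months.

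**How many are event-free.** The SAP 3.1.5.4 formula gives λ1 = −ln(1 − 0.223) / (31 + 0.3 × 150 + 0.2 × 185) = 0.2523 / 113 = 0.00223 per day. Assume mid-interval censoring, at days 105 and 272:

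- Day 105: exp(−0.00223 × (30 + 0.3 × 75)) = 0.889
- Day 272: exp(−0.00223 × (30 + 0.3 × 150 + 0.2 × 92)) = 0.812
- Event-free: 60 × 0.889 + 159 × 0.812 = 53.4 + 129.1 ≈ 182

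With assumed risk-graded rates of 36%, 22% and 8.5% (weighted: 0.35 × 36 + 0.30 × 22 + 0.35 × 8.5 = 22.2%) and follow-up spread evenly over each interval, the figure is about 191.

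**Removing those already at day 335.** If the 159 are spread evenly from day 180 to day 365, the event-free count below day 335 is 162 (flat rate) or 169 (graded). If they extend to day 395, the overdue limit in SAP 3.1.5.1, it is 147 or 153. SAP 7.3.2 limits this reduction: last follow-up is the latest recorded date, not the cutoff. A subject at calendar day 350 whose latest record is the 6-month visit still falls below 335. The range is therefore about 150 to 190 per arm.

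**True dropouts, per arm.** The full-cohort figure is 750 × 0.05 = 37.5. At the interim, assuming 5% per year accrued linearly: 530 × 0.05 = 26.5, plus 159 × 0.05 × 0.75 = 6.0, plus 60 × 0.05 × 0.29 = 0.9, or about 33. The 1-year cohort alone gives about 27.

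**Effect on the tipping count.** An illustrative simulation used Table 2 numbers, the graded rates, 5% dropout and equal arms. In 58 simulated trials non-inferiority was declared at the interim. The median tip is over trials that tipped, searched in steps of three events.

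| Pool treated as missing | Data entering the models | Mean missing, test arm | Trials that tip | Median tip |
|---|---|---|---|---|
| Dropouts only | Cohorts of 3.1.5.2 | 27 | 59% | 21 |
| Literal rule | Cohorts of 3.1.5.2 | 191 | 66% | 112 |
| Literal rule | All follow-up | 191 | 100% | 30 |

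The second and third rows differ because a subject censored at day 250 is outside the 181 to 365 day cohort. An event imputed at day 251 then either enters no model or enters one the subject does not belong to. The SAP does not say which.

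**The case against.** The strongest reply is that the intent is clear. The section is about dropouts, and every example describes someone whose year has ended, so a sensible programmer would leave ongoing subjects out. This stands in part: it makes the text ambiguous rather than a settled instruction to impute ongoing subjects. It does not close the gap. The rule is stated in days alone, the examples are not exhaustive, and no sentence mentions administrative censoring. The SAP 3.1.7 note allowing adjustments offers model convergence as its example and does not settle who is missing.

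A reader might also infer that a robust result would necessarily look fragile. The argument would be that about 20 extra test-arm events lose the threshold, which is only about 9% of a pool of 182 + 37 = 219, well under the 22.3% event rate. The documents do not support this. The ongoing subjects have already survived event-free, so only their remaining risk counts. On the flat-rate inputs, that risk to day 365 is 12.4% from day 105 and 4.1% from day 272: (53.4 × 0.124 + 129.1 × 0.041) / 182 ≈ 6.5%. The specified output is also a count, not a share, and on the cohort-restricted reading the count moves up. Nor can the dropout-only result be called very robust, since 59% of those simulated trials tipped.

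Finally, the consequence is limited. The primary test, its threshold and the decision do not change, and at the final analysis every subject has completed 1 year. That stands.

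**Conclusion.** The concern holds as a defect in a stated rule with an uninterpretable result under its literal reading. It is not evidence that the reported robustness will be wrong in a known direction. At an interim like that in Table 2, ongoing event-free subjects would outnumber true dropouts by roughly four to seven to one (about 150 to 190 against 27 to 37 per arm). The tipping count would not measure robustness to dropout and could err either way.

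The Table 2 sums and the 5% attrition are document figures. The stratum event rates, follow-up times and dropout timing are assumptions, and the simulation is small and illustrative. The issue arises only if non-inferiority is declared at the interim. It should be settled beforehand: SAP 4.3 places unblinding of the study team at that analysis, so choosing a reading afterwards would be post hoc.

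**What to change.** Amend SAP 3.1.7 before the formal interim, as SAP 5.8 allows.

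1. Define missing as no primary-endpoint event and last follow-up under 335 days from randomization, and in addition either (a) withdrew or was lost on or before the cutoff, or (b) 1-year follow-up complete under 3.1.5.1 (visit done early, recorded as not done, or overdue).
2. State that subjects still under follow-up at the cutoff are administratively censored and never imputed.
3. State which interval model an imputed event enters. This is still needed after items 1 and 2, because a subject who withdrew before reaching the next completion date can also lie outside the later cohort.
4. If non-inferiority is declared at the interim, repeat the tipping-point table once all subjects have 1-year data.

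The cost is a few sentences, one extra condition in the program and one additional table. Sample size, threshold and primary analysis stay as they are.
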